## 3.2 Exclusion Criteria

3.2.1 Severe COVID-19 is defined by one or more of the following:

- blood oxygen saturation  $\leq 90\%$
- partial pressure of arterial oxygen to fraction of inspired oxygen ratio  $< 300$
- lung infiltrates  $> 50\%$  within 24 to 48 hours

- 3.2.2 Life-threatening COVID-19 is defined as one or more of the following:
- respiratory failure
  - septic shock
  - multiple organ dysfunction or failure
- 3.2.3 Weight less than 45 kg.
- 3.2.4 Pregnant or breast-feeding females
- 3.2.5 Subjects on dialysis or with creatinine clearance < 45 ml/min
- 3.2.6 Existing DMID Toxicity Scale for Determining Severity of Adverse Events grade 3 or greater hepatic failure
- 3.2.7 Previously documented moderate or severe retinopathy or macular degeneration
- 3.2.8 Uncontrolled Seizure disorder
- 3.2.9 Known allergy to artemisia annua, artesunate, ivermectin, camostat mesilate, or other agents to be used in the trial.
- 3.2.10 Currently receiving any study medications for other indications
- 3.2.11 Concurrent use of medication that would cause moderate or severe due to drug-drug interactions with study medication.  
Specifically:
- Patients receiving **ivermectin** may not be concurrently taking strong CYP3A4/ABCB1 inhibitors (Azole antifungals including voriconazole, ketoconazole, itraconazole and posaconazole; clarithromycin, telithromycin, nefazodone, saquinavir, darunavir, or lopinavir, etc.)
  - Patients receiving **Artemisia annua tea or coffee OR artesunate** may not be currently taking strong inducers of CYP2A6, including phenobarbital and rifampin.[59]
- 3.2.12 Receipt in the 12 hours prior to enrollment, or planned administration during the 14-day study period that treating clinicians feel cannot be substituted for another medication, of any of the following: amiodarone; cimetidine; dofetilide; phenobarbital; phenytoin; or sotalol.
- 3.2.13 Cancer patients receiving active immunosuppressive treatment cannot enrolled unless they are on a treatment holiday with no antineoplastic treatment with 3 weeks of

enrollment.

Enrollment on other experimental therapies for COVID19

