3.1.4 Ability to provide informed consent by the patient or healthcare proxy

3.1.5 Ability to return for repeated testing and observation to UKHC

3.1.6 Patients must have adequate organ and marrow function measured within the last 30 days as defined below:

- platelets  $\geq 100,000/\text{mcL}$
  - AST(SGOT)/ALT(SGPT)  $\leq 3 \times$  institutional ULN
  - creatinine  $\leq 1.5 \times$  institutional ULN
- OR
- glomerular filtration rate (GFR)  $\geq 45 \text{ mL}/\text{min}/1.73 \text{ m}^2$  unless data exists supporting safe use at lower kidney function values, no lower than  $30 \text{ mL}/\text{min}/1.73 \text{ m}^2$  (see Appendix B).

3.1.7 The effects of therapeutic agents used in this trial on the developing human fetus are unknown. Because therapeutic agents used in this trial may be teratogenic, women of child-bearing potential and men must agree to use adequate contraception (hormonal or barrier method of birth control; abstinence) prior to study entry and for the duration of study participation. Should a woman become pregnant or suspect she is pregnant while she or her partner is participating in this study, she should inform her treating physician immediately. Men treated or enrolled on this protocol must also agree to use adequate contraception prior to the study, for the duration of study participation.

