#### 4.9 Patient Registration to Treatment

To register a patient, the following information should be reviewed by the clinical research nurse (CRN) / clinical research associate (CRA) with the study physician per MCC SOPs to confirm eligibility:

- Copy of COVID19 testing results
- Mobile EKG tracing (outpatients) or standard EKG (inpatients) within 5 days of registration to assess QTc interval
- Eligibility labs, as well as correlative labs to be drawn
- Eligibility Checklist

Once eligibility is confirmed, the CRN/CRA will complete subject registration in the OnCore database (minimum data footprint) for randomization and complete study-required RedCap data forms. To complete the registration process, the CRN/CRA will:

- assign a patient study number
- register the patient on the study in OnCore
- receive the automated treatment arm assignment
- send an email or other communication to the study team of arm assignments.

If a patient is deemed ineligible for treatment their specimens will be retained in the COVID19 BIOBANK if the subject has indicated agreement to specimen collection and long-term storage in the consent form.

At the Day 1 visit or inpatient the following will be completed

- 1) Sign **treatment informed consent** (unless previously e-consented as above)
- 2) Undergo blood testing for eligibility (in subjects who have not had assessment of screening labs within the last 30 days will require blood draw)
- 3) Complete an eligibility questionnaire (age, concurrent diseases, current medications, contact information)
- 4) Undergo a mobile EKG or standard EKG tracing to assess QTc interval (within 5 days of registration)
- 5) Distribute medications, pill diary, and instructions
- 6) Baseline correlative blood sample
- 7) Sputum sample, with OP swab (alternative, if no sputum available)
- 8) Saliva sample
- 9) COVID-19 ordinal scale assessment (See Appendix B)
- 10) Limited visual physical exam unless a more complete exam is clinically indicated.

Day 3 or 4 phone call to assess clinical status and elicit concerns or questions.

Day 7 telehealth (+/- 4 days) is required for all patients to assess toxicity. If a subject has a standard of care telehealth visit during this period, this is also an acceptable toxicity assessment.

Day 10 or 11 phone call to assess clinical status and elicit concerns or questions

Day 14 (+/- 4 days) visit will also be completed in clinic or inpatient hospital.

- 1) Undergo blood testing for toxicity

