#### **6.4 Duration of Follow-Up**

Patients will be followed for up to 40 days from the beginning of therapy or until death, whichever occurs first.

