**Rare known potential toxicities, <1% (Limited to important or life-threatening):**

Hyperbilirubinemia

Hypersensitivity

Pregnancy: There is insufficient evidence to prove safety. Based on the animal and human data ivermectin is labeled category C in the US (animal EFD finding, but only at doses also toxic to the pregnant female). The manufacturer considers it contraindicated in pregnancy.

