**10.9 Pregnancy**

Pregnancy is considered an unanticipated event and pregnancy as well as its outcome must be documented and reported to overall PI and DSMC and Office of Research Integrity, as well the FDA and sponsor in according to reporting requirements. Any pregnancy occurring in a patient or patient's partner from the time of consent to 90 days after the last dose of study drug must be reported and then followed for outcome. Newborn infants should be followed until 30 days old.

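### Pregnancy is an exclusion and the agents are described as possibly teratogenic, but the protocol names no pregnancy test before dosing

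*Combined protocol and SAP*

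**What the plan says.** Section 3.2.4 excludes "Pregnant or breast-feeding females". Section 3.1.7 describes fetal effects as not known and goes on: "Because therapeutic agents used in this trial may be teratogenic, women of child-bearing potential and men must agree to use adequate contraception". The contraception requirement starts before entry and lasts for study participation, and a woman who becomes or suspects she is pregnant is to tell her physician. Pregnancy is also a reason to end treatment (6.3).

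The drug sections differ by agent. For ivermectin, 8.1.3 states: "The manufacturer considers it contraindicated in pregnancy". For camostat, 8.1.4 says the evidence is not enough to establish safety in pregnancy. Sections 8.1.5 (Artemisia annua) and 8.1.6 (artesunate) both describe use in pregnant women with malaria as safe.

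On laboratory eligibility, 3.1.6 says: "Patients must have adequate organ and marrow function measured within the last 30 days as defined below". It then lists platelets, AST/ALT, and creatinine or GFR. The Day 1 list in 4.9 includes "Undergo blood testing for eligibility", with a new draw only for patients who have no screening labs from the previous 30 days.

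On reporting, 10.9 covers any pregnancy in a patient or partner "from the time of consent to 90 days after the last dose of study drug". Section 6.4 says: "Patients will be followed for up to 40 days from the beginning of therapy".

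**The concern.** An exclusion made for fetal safety needs a stated means of verification. Women from age 18 with a single risk feature such as BMI of 30 or more, diabetes or moderate to severe asthma can enter (3.1.1, 3.1.3), and 3.1.7 expressly anticipates women of child-bearing potential. If the listed procedures contain no test, a pregnancy that neither the patient nor her record discloses would pass through eligibility unnoticed, and drug could be given to someone the protocol means to exclude. Separately, a duty to report pregnancies for 90 days after the last dose depends on someone asking, and follow-up stops well before that.

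**Working it through.** This is mainly a reading check. Arithmetic enters only at step 6.

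1. **Every list of pre-dose procedures.**
   - 3.1.6: platelets, AST/ALT, creatinine or GFR. No hCG.
   - 4.9, registration: COVID-19 result, EKG, eligibility labs, eligibility checklist. The last two are not itemised.
   - 4.9, Day 1: consent, conditional eligibility bloods, a questionnaire, EKG, drug distribution, research samples, ordinal scale and a mainly visual examination. The questionnaire's stated contents are age, diseases, medications and contact details; pregnancy status is not among them.
   - Section 11: rows for CBC, CMP and EKG. No pregnancy-test row at any visit.

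2. **Other safeguards.** Eligibility is reviewed from the medical record (11) and confirmed with the study physician (4.9). These steps find a pregnancy that is known or recorded. The contraception agreement lowers the chance of pregnancy without verifying status at entry. The stopping reason in 6.3 can act only on a pregnancy that has been recognised.

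3. **Timing in Arm C.** Ivermectin is taken on Days 1 and 2 (6.1). The first follow-up contact is on Day 3 or 4 (4.9, 11), after the course has ended.

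4. **Which sample could carry a test.** Eligibility bloods are not redrawn when labs from the last 30 days exist. The Day 1 blood meant for every patient is correlative. It goes to a research facility or biobank, may be processed up to 24 hours after the draw, and is received Monday to Friday (5.1, 5.3). Study drug is distributed at the same visit (4.9). The documents therefore do not show that this blood could give a result before dosing.

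5. **Fetal-risk statements side by side.** Section 3.1.7 treats all agents as of unknown effect and possibly teratogenic. Sections 8.1.5 and 8.1.6 call two of the four safe in pregnancy. These do not agree.

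6. **Reporting window against follow-up**, assuming dosing starts on Day 1 without interruption. The window ends on the last dosing day + 90.
   - 14-day arms: 14 + 90 = about Day 104.
   - Ivermectin: 2 + 90 = about Day 92.
   - Beyond the 40-day maximum: 104 − 40 = 64 days, or 92 − 40 = 52 days.
   - Beyond Day 28: 104 − 28 = 76 days, or 92 − 28 = 64 days.

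   Day 28 matters because the Day 40 visit is conditional on serology and viral results and is labelled optional in 4.9, so the last routine visit is Day 28. Section 6.1 mentions weekly phone contact for clinical outcomes with no stated end. Even if the calls continue as long as 6.4 allows, they stop at Day 40, and the calendar shows none after Day 10 or 11.

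**The case against.** The strongest reply is that absence from the text is not absence from practice. The eligibility labs and checklist in 4.9 are not spelled out, the flow figures in Appendices D to F are not visible, and a test could sit in any of these. That stands as a limit: the supportable claim is that the protocol text and calendar do not require a test.

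Several stronger readings are tempting, and the documents do not support them:
- *The exclusion rests on self-report alone.* Record review and physician confirmation also apply.
- *Pregnant women would be randomized and treated.* The text shows only that an unrecognised pregnancy might not be detected. The number of women of child-bearing potential is not given, and age 50 or over is by itself a qualifying risk feature.
- *The risk is the same in all four arms.* The contraindication is the manufacturer's view and concerns Arm C only. The text on camostat is inconclusive, and the other two agents are called safe.
- *The reporting duty cannot be met.* Section 10.9 carries its own follow-up of known pregnancies to outcome, and of newborns to 30 days of age, so it already reaches beyond 6.4 once a pregnancy is known. A contraception period shorter than a reporting window is not in itself a contradiction. What remains is that no scheduled contact would elicit pregnancies late in the window.

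**Conclusion.** The point holds in this limited form: a stated safety exclusion has no verification step named in the protocol, and the listed procedures would not reliably find an unrecognised early pregnancy before dosing. Arm C is the sharpest case, because it combines the manufacturer's contraindication with a course that is finished before any follow-up contact. How many patients this affects cannot be estimated from the documents. The primary endpoint, the 60 patients per arm, the maximum of 240 and the planned analysis are unaffected. This is an eligibility and safety gap that should be closed, and it is not a flaw in the statistical design.

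The reporting mismatch is a lesser matter. The window outlasts the longest possible follow-up by about 64 days with 14-day dosing and about 52 days with ivermectin, and by more for patients whose last visit is Day 28. These figures assume uninterrupted dosing from Day 1. The conclusion about testing assumes that no test is required by a form outside the protocol.

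**What to change.** Add a urine or clinical-laboratory serum hCG for women of child-bearing potential to the eligibility list in 4.9, and a matching row to the calendar under Pre-Study/Day 1. Require the result before registration and randomization, and in any case before study drug is distributed, including before an Arm E shipment is ordered. A result before randomization also avoids randomizing someone who is then not dosed and so falls outside the m-ITT population in 9.5. State how old the result may be, since 4.10 allows up to 7 days from registration to treatment. Do not rely on the correlative research blood.

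If a test is already required by a form outside the protocol, cite that form in 4.9 and in the calendar.

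Reconcile 3.1.7 with 8.1.5 and 8.1.6 on fetal risk. Reconcile 10.9 with 6.4 by stating how pregnancies in patients or partners will be elicited after the last scheduled contact.

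The cost is one inexpensive test in a subset of patients, a urine or clinical blood sample for those whose eligibility labs are not redrawn, one calendar row and some text edits. If a late contact is chosen to cover the reporting window, that adds a call. No change to sample size or analysis is needed.

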3.2.14 Inability to receive enteral medications

3.2.15 Patients with psychiatric illness/social situations that would limit compliance with study requirements.

3.2.16 Any other condition that in the opinion of the treating physician justifies exclusion from the study.

### **3.3 Inclusion of Women and Minorities**

NIH policy requires that women and members of minority groups and their subpopulations be included in all NIH-supported biomedical and behavioral research projects involving NIH-defined clinical research unless a clear and compelling rationale and justification establishes that inclusion is inappropriate with respect to the health of the subjects or the purpose of the research. Cost is not an acceptable reason for exclusion except when the study would duplicate data from other sources. Women of childbearing potential should not be routinely excluded from participation in clinical research. Please see <http://grants.nih.gov/grants/funding/phs398/phs398.pdf>.

## **4. INVESTIGATOR REQUIREMENTS AND REGISTRATION PROCEDURES**

### **4.1 Investigator and Research Associate Registration with MCC**

All investigators must be qualified by education, training and experience to assume responsibility for the proper conduct of human subject research. Investigators are responsible for being able to provide evidence of such qualifications through up-to-date curriculum vitae and/or other relevant documentation and training per institutional, state and federal guidelines. All investigators conducting MCC trials will complete all requisite training and registrations per MCC SOPs.

### **4.2 Clinical Trial Registration with [clinicaltrials.gov](http://clinicaltrials.gov) and release of trial results**

Contact the MCC-CRO Regulatory unit at [[contact]](mailto:[contact]) if you need assistance in completing your [clinicaltrials.gov](http://clinicaltrials.gov) registration. **Results will be released on [clinicaltrials.gov](http://clinicaltrials.gov) according the data guidelines and requirements of [clinicaltrials.gov](http://clinicaltrials.gov).**

### **4.3 Enrollment Guidelines**

Eligible patients will be identified by the principal investigator and co-investigators of this study. Potentially eligible patients will be screened via multiple testing sites as outlined in Appendix F. Patients will be evaluated at the University of Kentucky by the investigators and study personnel with oversight by the Principal Investigator (PI). Upon obtaining proper consent to treatment, patients will be enrolled into the study.

#### **4.4 Delegation of Tasks Log (DTL)**

All MCC studies require a Delegation Task Log which is maintained by the MCC Regulatory Unit of the Clinical Research Office.

In order to be added to the DTL for a given study, each staff member must have appropriate training to conduct assigned duties including but not limited to protocol specific training and review of the final protocol.

#### **4.5 Informed Consent**

The goal of the informed consent *process* is to provide people with sufficient information so they can make informed choices about whether to begin or continue participation in clinical research. The process involves a dynamic and continuing exchange of information between the research team and the participant throughout the research experience. It includes discussion of the study's purpose, research procedures, risks and potential benefits, and the voluntary nature of participation.

The informed consent *document* provides a summary of the clinical study and the individual's rights as a research participant. The document acts as a starting point for the necessary exchange of information between the investigator and potential research participant. Also, research participants and their families may use the consent document as an information resource and reference throughout participation in the trial. The informed consent *document* is often considered the foundation of the informed consent process; it does not, however, represent the entirety of the process. Nor is the informed consent document a risk-management tool for the investigator and/or institution.

The investigator must explain to each subject (or legally authorized representative) the nature of the study, its purpose, the procedures involved, the expected duration, the potential risks and benefits involved and any discomfort it may entail. Each subject must be informed that participation in the study is voluntary and that he/she may withdraw from the study at any time and that withdrawal of consent will not affect his/her subsequent medical treatment or relationship with the treating physician.

#### **4.6 Recruitment Plans:**

##### **Inpatient Recruitment**

Inpatients will be screened by their treating physician team, informed of the study and if interested in participating, will be approached by study staff for review of eligibility and informed consent.

##### **Outpatient Recruitment:**

- *Initial study presentation: Appendix D, E*
  - Phone or telehealth contact to prospective outpatients who are being referred for testing at the University of Kentucky

- Prescreening from screening lists (section 4.5.3)
- Presentation of study to patient
- Assessment of patient interest in participation
- Directing interested patients to Research Designated Clinic or drive-through
- OR, walk in patient presenting to Research Designated Clinic
- OR to a telehealth consent conference
  
- *Research Designated Clinic:* University of Kentucky ambulatory care clinics that are:
  - Designated for testing and management of COVID-19 and its complications
  - Provides testing, evaluation, and treatment site adhering to current CDC and University of Kentucky COVID-19 guidelines for the provision of ambulatory care
  - Intended to enable recruitment and participation in research studies
  - Has the ability to obtain the nasopharyngeal swabs, blood samples, electrocardiograms (EKGs), and additional study related evaluations required for safety/tolerability and outcomes monitoring associated with this study
  
- *Study intake procedures: Appendix F*
  - Research Designated Clinic presents study and obtains either consent or decline to participate
    - Enroll consenting patients in study
    - Provide declining patients full scope of routine care for COVID-19 patients

#### **4.7 Patient Screening Options**

All individuals who are tested for COVID-19, via a drive through testing facility of the University of Kentucky, other testing sites sanctioned by the Kentucky Department of Health, any outpatient clinic associated with UKHC, or admitted to UKHC inpatient hospitals will be eligible for screening. If a screening consent is used, individuals willing to be screened will consent to the following:

- 1) Agree to allow study staff to review clinical COVID19 test results, baseline eligibility, labs, via medical records review
- 2) Agree to be re-contacted for study participation and future contact for possible plasma donor status.

Research staff will register screened patients into a password protected RedCap database.

#### **Screening can be done via one of the following ways:**

- 4.7.1 Face-to-face screening outside of clinic or inpatient (i.e. drive through test facility, nursing home setting, etc.). In this setting, patients will be given a screening consent.
- 4.7.2 Remote screening via referral from the University of Kentucky outpatient COVID-19 monitoring programs, including the GetWell Loop (an automated patient health monitoring tool, Appendix E), other testing systems or through phone or telehealth mechanisms, whether centralized or in association with specific clinics or clinical

entities, will be eligible to be asked if they are interested in enrollment in participating in research and will be electronically consented via RedCap and will be referred to research designated sites for treatment consent and evaluation as appropriate.

- 4.7.3 Waiver of consent for screening – The study team will be provided a list of all people testing positive for COVID-19 by the University of Kentucky outpatient COVID-19 monitoring program who have agreed to be contacted for this research study. Research staff will review this list of subjects, screen for the high risk categories which would make them eligible and contact the patient and offer participation in the trial via remote means. Those that meet entry criteria, and agree to participate will then have an informed consent conference with the PI or co-I, a CRA electronically (remotely, or in person) and e-sign the treatment consent via remote RedCap consent process. They will then be directed to the research clinic for specimen collection and clinic visit.
- 4.7.4 Direct screening – Patient’s treating physician will be approached regarding eligibility and appropriateness for participation in this trial.
- 4.7.5 Face-to-face screening outside of clinic or inpatient will occur at those testing sites where people can be approached for potential participation but cannot be fully assessed for eligibility. In these cases, a screening consent will be used

